Demographics/Medical history/Prior medications, non-drug therapies, and radiotherapy/Height	N/A										This information will be transferred from prior studies
Vitals	Vital signs and weight		X ^c	X	X	X	X	X	X		
PRO instruments	EQ-5D-5L		X ^c	X	X	X	X	X	X		Performed before any physical tests
	PROMIS PF		X ^c	X	X	X	X	X	X		Physical Function Scale performed before any physical tests
Safety	Physical exam		X ^c	X	X	X	X	X	X		Full PE at Screening and EOS, abbreviated PE at other visits. All PEs will include functional assessment for the affected joint.
	ECG		X ^c						X		May be performed whenever deemed medically necessary and at any visit during which a subject exhibits a heart rate ≤ 50 bpm. Any abnormal finding should be confirmed with a repeated ECG. ECGs should be performed after vital signs assessments.
AE	AE/SAE		X ^c			X			X		
Concomitant medications, non-drug therapies, and radiotherapy	Concomitant		X ^c			X					

	Visits	SCR	BL	M1	M3/ M15	M6/ M18	M9/ M21	M12 ^a	M24	EOS/ AE F/U ^b	Comment
	Window (Days)	0*	0*	+ 28	±14	±14	±14	±14	±14	±7	** SCR and BL will both occur on EOT visit of preceding study.
Assessments	Procedure										
Laboratory assessments	Hematology		X ^c			X		X	X		See Section 10.2 for details
	Chemistry		X ^c			X		X	X		See Section 10.2 for details
	Urinalysis		X ^c			X		X	X		See Section 10.2 for details
	Coagulation		X ^c			X		X	X		See Section 10.2 for details
	Liver function tests		X			X		X	X		AST, ALT, ALP, total bilirubin, GGT, direct bilirubin
	Urine pregnancy test	X									
	Hormone testing	X ^c	X ^c								Females only, FSH to confirm postmenopausal status
	TSH	X									
Disease assessment	MRI of affected joint		X ^c	X	X	X	X	X	X		Tumor assessment
Dosing Diary	Provide Diary		X	X	X	X	X	X			Diary for AEs between scheduled clinic visits
	Review Diary			X	X	X	X	X	X		
EOS Form										X	

AE = adverse event; BL = baseline; D = day; ECG = electrocardiogram; EOS = End of Study; EOT = End of Treatment; EQ 5D 5L = European Quality of Life Five Dimension Five Level Scale; FSH = follicle stimulating hormone; FU = Follow-up; M = month; MRI = magnetic resonance imaging; PRO = Patient-Reported Outcome; PROMIS PF = Patient-Reported Outcomes Measurement Information System – Physical Function; SAE = serious adverse events; SCR = screening; TVS = tumor volume score.

Note: For all visits, a month is considered a 30-day interval.

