6.6. Prior and Concomitant Medications

During the study, if the use of any concomitant treatment becomes necessary (e.g., for treatment of an AE), the treatment must be recorded on the source document and eCRF, including the reason for treatment, name of the drug, dosage, route, and date of administration. All medications including prescription, over-the-counter (OTC), herbal and other nutritional vitamins and/or supplements taken within 30 days of the Baseline visit will be recorded on the eCRF. Note that vaccinations for COVID-19 are to be recorded on the source document and captured on the eCRF under both the concomitant medications section and on the COVID-19 forms.

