6.7.2. Acid-reducing Agents

Avoid the concomitant use of proton pump inhibitors (PPIs) while taking pexidartinib. As an alternative to a PPI, administer pexidartinib 2 hours before or 2 hours after taking a locally-acting antacid, or if using a histamine 2 (H2)-receptor antagonist, administer pexidartinib at least 2 hours before or 10 hours after taking an H2-receptor antagonist.

Permitted Therapies/Products

Subjects are permitted to receive prophylactic or supportive treatment as standard of care during treatment, per Investigator's discretion and institutional guidelines.

- Palliative radiation to non-measurable lesion is permitted as long as the radiation field does not include measurable lesion;
- Investigators' discretion is recommended for the following:
 - Prophylactic or supportive treatment for expected toxicities, including management of study drug will be as per Investigator's discretion.

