7. STUDY DRUG DISCONTINUATION AND DISCONTINUATION FROM THE STUDY

This section describes subjects who discontinue pexidartinib treatment as part of this study for reasons listed below and **NOT** subjects who are participating in the Treatment-Free period of the **Treatment-Free/Re-Treatment Cohort**.

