9.5. Statistical Analysis

The Statistical Analysis Plan (SAP) will be developed and finalized before database lock and will describe the subject populations to be included in the analyses, and procedures for accounting for missing, unused, and spurious data. This section is a summary of the planned statistical analyses of the primary and secondary endpoints.

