9.5.1. Efficacy Analyses

Table 3.1 and **Table 3.2** list the primary and secondary endpoints and their corresponding definitions of all endpoints. Additional details for the analysis and censoring rules are noted in the following sections. Detailed censoring rules for the primary and applicable secondary efficacy endpoints will be specified in the SAP.

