9.5.1.1. Primary Efficacy Analyses

The primary endpoint in this study is the proportion of subjects who remain treatment-free at Month 12 and Month 24 after entering the Treatment-Free period in the **Treatment-Free/Re-Treatment Cohort**. The primary efficacy analysis will be based on the data from the FAS.

Kaplan-Meier methods will be used to estimate the proportion of subjects who remain treatment-free at Month 12 and Month 24. Estimate of the proportion will be provided with its 95% confidence interval (CI) using Greenwood's formula.

The subjects who resume pexidartinib treatment or died will be considered as an event. The subjects who take subsequent systemic therapy or undergo surgery for the treatment of TGCT will also be counted as an event. The subjects who withdraw consent or lost to follow up will be censored at the last contact date.

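### The primary event rule in Section 9.5.1.1 counts systemic therapy and surgery for TGCT but not radiotherapy or other local therapy, so a subject irradiated for TGCT would not be an event

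*Combined protocol and SAP*

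**What the plan says.** Section 9.5.1.1 estimates the proportion treatment-free at Month 12 and Month 24 by Kaplan-Meier in the Full Analysis Set of the Treatment-Free/Re-Treatment Cohort. Restarting pexidartinib and death are events. The rule then adds: "The subjects who take subsequent systemic therapy or undergo surgery for the treatment of TGCT will also be counted as an event". On censoring it says: "The subjects who withdraw consent or lost to follow up will be censored at the last contact date". Radiotherapy appears in neither sentence.

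Other places bear on the point:

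- Table 1.2, the schedule for the Treatment-Free period, has a collection row labelled "Concomitant medications, non-drug therapies, and radiotherapy".
- Section 6.6 requires any concomitant treatment to be recorded, "including the reason for treatment, name of the drug, dosage, route, and date of administration".
- Under the permitted therapies that follow Section 6.7.2: "Palliative radiation to non-measurable lesion is permitted as long as the radiation field does not include measurable lesion". The lead-in to that list concerns care given during treatment.
- Section 7 states that its discontinuation reasons do not describe "subjects who are participating in the Treatment-Free period".
- Section 9.5.1: "Detailed censoring rules for the primary and applicable secondary efficacy endpoints will be specified in the SAP". Section 9.5 adds: "This section is a summary of the planned statistical analyses of the primary and secondary endpoints".
- Section 4.1.1, Table 1.1 footnote e and Table 1.3 footnote f time a final MRI relative to the start of any new TGCT therapy, with surgery given as one example of it.

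**The concern.** Because surgery and other systemic drugs count as events, treatment-free in this endpoint means more than free of pexidartinib: it means free of treatment for TGCT. Radiotherapy given for TGCT is also treatment for TGCT, and the plan collects it as a named item in the period that the endpoint covers. The event rule omits it and gives no reason.

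Two subjects whose tumor needed a local intervention in the Treatment-Free period would therefore be classified in opposite ways, according to whether that intervention was an operation or radiation. The error can only raise the proportion or leave it unchanged. The study has no hypothesis test, and this proportion is the primary efficacy result, so it would be read directly as the share of patients who can stop treatment. The study is also open-label. If the rule is left silent, someone will have to decide how to classify an irradiated subject after the data are known.

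**Working it through.** The plan gives no cohort size, expected event rate or radiotherapy frequency, so there is no figure of its own to reproduce. The check has two parts: apply the rule to the cases, then size the result on stated assumptions.

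**1. The rule applied to four subjects, each still in follow-up at the landmark**

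| What happens in the Treatment-Free period | Status under Section 9.5.1.1 |
|---|---|
| Restarts pexidartinib | Event |
| Takes another systemic therapy for TGCT | Event |
| Has surgery for TGCT | Event |
| Has radiotherapy for TGCT, nothing else | Not an event; no censoring rule stated |

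No other section changes the last row. Section 7 sets aside Treatment-Free subjects, the radiation bullet after Section 6.7.2 governs what is permitted during treatment, and Section 9.5.1 leaves censoring rules, not the event list, to the SAP.

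**2. Size without censoring before the landmark**

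Kaplan-Meier reduces to S = 1 − d/n, with d events among n subjects. Counting one irradiated, otherwise event-free subject changes d to d + 1, so the difference is (1 − d/n) − (1 − (d + 1)/n) = 1/n, whatever d is.

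Assumed n (61 is the number still on treatment in two of the four feeder studies at an earlier cut-off, Section 2.1.2, and is not a cohort size):

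- n = 12: 1/12 = 8.3 points
- n = 20: 1/20 = 5.0 points
- n = 30: 1/30 = 3.3 points
- n = 61: 1/61 = 1.6 points

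At n = 20, as written against counted: no restarts, 100% v 95%; five restarts, 75% v 70%; ten restarts, 50% v 45%.

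**3. Others censored earlier**

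If c other subjects are censored before the irradiation and nobody restarts, the difference is 1/(n − c). At n = 20: c = 2 gives 1/18 = 5.6 points; c = 4 gives 1/16 = 6.3 points.

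**4. The irradiated subject later restarts pexidartinib**

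n = 20, irradiated at month 7, restart at month 18, no other events. Month 12: 100% as written v 95% counted. Month 24: 95% either way. The effect at a landmark disappears once the subject has a listed event before it.

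**5. If the SAP censored at radiotherapy instead**

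n = 20, one subject irradiated at month 7, five others restart by Month 12.

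- Counted as an event: 14/20 = 70.0%.
- Not an event and not censored: 15/20 = 75.0%.
- Censored at month 7, all restarts before then: 15/20 = 75.0%.
- Censored at month 7, all restarts after then: 1 − 5/19 = 14/19 = 73.7%.

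Censoring leaves the estimate 3.7 to 5.0 points above the value that the same subject would give if operated on. It does not restore equal treatment.

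**The case against.** The best case against rests on five arguments.

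*The SAP may deal with it.* Section 9.5 calls itself a summary, Section 9.5.1 leaves detailed censoring rules to the SAP, and the censoring sentence in Section 9.5.1.1 is plainly incomplete, since it does not mention subjects who reach the end of follow-up treatment-free. This stands in part. A reader might infer that an irradiated subject is definitely never censored; the documents do not support that, because a censoring rule could still be written. What they do fix is the event list, and step 5 shows that censoring is not equivalent to it.

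*No text says that irradiated subjects count as treatment-free.* Correct. Table 3.1 says only that subjects remain treatment-free. The result follows from applying an explicit list that leaves radiotherapy out, not from a stated intention.

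*The case is not expected.* Section 2.1.1 describes surgery and systemic therapy, the two kinds of treatment the rule names. The radiotherapy row has the same label in Tables 1.1, 1.2 and 1.3, so it may be a general collection field. The permitted radiation excludes fields that cover a measurable lesion. The reference list does include a paper whose title concerns radiation for high-risk pigmented villonodular synovitis, but that gives no frequency. This argument limits the likely size. It does not supply a classification if the case occurs, even as a deviation.

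*Any reclassified subject moves a proportion by 1/n.* True. The arithmetic gives the scale and direction, not evidence that the case will arise.

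*Adding radiotherapy alone would be too narrow.* This stands. Other non-drug therapies sit in the same collection row, so the fix should use the wider class of any new TGCT therapy.

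**Conclusion.** The point holds as a defect in a stated rule: the event list for the primary efficacy endpoint omits radiotherapy and other local therapy for TGCT, and so treats an irradiated subject differently from an operated one. The overstatement at Month 12 or Month 24 is about 1/n for each irradiated subject with no other event by that landmark. It is exactly 1/n without earlier censoring, somewhat more with it, and zero if a listed event has already occurred. On assumed cohorts of 12 to 61 this is 8.3 down to 1.6 points per subject. Cohort size and frequency of use are unknown, and the effect is nil if nobody is irradiated for TGCT.

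Two stronger readings are not supported. A reader might infer that the results will be biased; the documents show only that they could be. A reader might also infer that the treatment-free proportion is the whole primary result. The objectives tables (synopsis, and Tables 3.1 and 3.2) also label the adverse event counts as primary outcome measures, so the point concerns the primary efficacy proportion only.

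**What to change.** In Section 9.5.1.1, replace the second event sentence with one that counts as an event *any new TGCT therapy, including subsequent systemic therapy, surgery or radiotherapy*. This matches the wider term that the protocol already uses when it times the final MRI. Date the event at the start of that therapy, from the concomitant-therapy and radiotherapy record in Table 1.2, and carry the same definition into the SAP before database lock.

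The cost is one phrase and no new assessment. One check is needed: Section 6.6 asks for reason and date for any concomitant treatment but is worded for drugs, so confirm that the eCRF radiotherapy entry captures both indication and start date. If it does not, those fields must be added or queried. The downside is that the reported treatment-free proportion may be lower.

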9.5.1.2. Secondary Efficacy Analyses

The PRO measures will be summarized descriptively over time along with its 95% CI by each cohort. The mean change from Baseline for these measures will also be reported over time along with its 95% CI by each cohort. The analysis will be conducted in the Evaluable Analysis Set (EAS).

Similar analyses will be conducted in the Re-treatment Analysis Set subjects (RAS). In this analysis, the Baseline measure of the retreated subjects is defined as the latest measure prior to or on the date of re-treatment of pexidartinib.

Qualitative assessments of the tumor will be summarized descriptively for pexidartinib re-treated subjects in the **Treatment-Free/Re-Treatment Cohort** and for all subjects in the **Treatment Continuation Cohort**.

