2. Subjects who choose to discontinue pexidartinib treatment will be enrolled into the Treatment-Free period of the **Treatment-Free/Re-Treatment Cohort**. The assessments from the subject's End-of-Treatment visit from their prior study (eg, tumor assessments, PRO measures, and safety parameters) will serve as the Baseline measurements for PL3397-A-U4003 study. Subjects will discontinue pexidartinib treatment and undergo clinical assessments at 3-month intervals during the Treatment-Free period. Re-treatment with pexidartinib will be based on the discretion of the subject and Investigator. Tumor assessment, subjective and/or functional measures, and safety will be considered in the decision-making process. The rationale for discontinuing and restarting pexidartinib re-treatment will be recorded accordingly.

Subjects in the **Treatment-Free/Re-Treatment Cohort** who enter the Re-Treatment period will be administered pexidartinib at the dose at which they completed the prior study. Dosing is required on an empty stomach (at least

1 hour before or 2 hours after a meal or snack), at approximately the same times of the day, and approximately 12 hours apart. During the Re-Treatment period, Investigators will ensure weekly liver monitoring tests for the first 8 weeks (2 months), then every 2 weeks for 1 month, then once every 3 months or more frequently as directed by the Investigator.

The Investigator will evaluate the MRI scans every 6 months for subjects in the Treatment Continuation Cohort and every 3 months for subjects in the Treatment-Free/Re-Treatment Cohort to perform a qualitative tumor assessment (i.e., stable disease) for subjects in the Treatment Continuation Cohort. Additional imaging assessments may be performed with changes in tumor response(s) as deemed necessary by the Investigator.

Patient Reported Outcomes (PROs) measures will be performed at 3-month intervals for all subjects.

Ongoing safety assessment, laboratory assessments (serum chemistry and hematology), and physical examination will be performed at 3-month intervals and monitored for adverse events (AEs). Note that laboratory assessments for urinalysis will be performed at 6-month intervals.

See [Figure 1.1](#) for the study flow diagram.

Study Duration

The study start is the date when the first subject has signed the informed consent. Subjects will be evaluated for eligibility at the last visit of their prior study.

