3. OBJECTIVES, OUTCOME MEASURES, AND ENDPOINTS

The objectives, definitions of associated endpoints, as well as applicable outcome measures are described in [Table 3.1](#) and [Table 3.2](#). Further requirements for the endpoint analyses and censoring rules, where applicable, can be found in [Section 9.5.1](#), [Section 9.5.2](#), and [Section 9.5.3](#).

Table 3.1: Description of Objectives, Outcome Measures, and Endpoints (Treatment-Free/Re-Treatment Cohort)

Period	Objectives	Outcome Measure	Endpoints	Category
Primary Objective				
Overall	Proportion of subjects who remain treatment-free	
Title: Proportion of treatment-free subjects at 12 months and 24 months
 
Description: Proportion of subjects who remain treatment-free at Month 12 and Month 24
 
Time frame: 24 months after last subject enrolled in the Cohort
	Proportion of subjects who remain treatment-free at Month 12 and Month 24	Efficacy
Secondary Objectives				
Treatment-Free period	Change from Baseline in Patient Reported Outcomes (PROs)	
Title: Change from Baseline in PROs
 
Description: Change from Baseline in PROs (PROMIS PF, EQ-5D-5L)
 
Time frame: 24 months after last subject enrolled in the Cohort
	Mean change from Baseline* for PROMIS PF and EQ-5D-5L quarterly for the treatment-free and Re-Treatment periods. *Note: Baseline is Screening values.	Efficacy
	Safety	
Title: Number of subjects with AE during the Treatment-Free period*
 
Description: Total number of subjects in the safety analysis set with any AE collected between Screening and start of re-treatment or final database lock (whichever occurs first)
 
Time frame: 24 months after last subject enrolled in the Cohort
 
*Note: Listed as a secondary objective but is a primary outcome measure.
	Incidence of AEs and SAEs, ECGs, and laboratory assessments	Safety
Re-Treatment period	Tumor Assessment	
Title: Tumor assessment
 
Description: Investigator evaluation of tumor
 
Time frame: 24 months after last subject enrolled in the Cohort
	Qualitative assessment of the tumor	Efficacy

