9.4. Population for Analysis Sets

Analysis Sets

- The Safety Analysis Set will include all subjects who entered this study. Subjects will be analyzed according to their cohort (**Treatment-Free/Re-Treatment Cohort; Treatment Continuation Cohort**).
- The Full Analysis Set (FAS) for the **Treatment-Free/Re-Treatment Cohort** will include all subjects who entered the Treatment-Free/Re-Treatment Cohort. This data set will be the primary population for the primary endpoint.
- The Full Analysis Set (FAS) for the **Treatment Continuation Cohort** will include all subjects who entered the Treatment Continuation Cohort.
- The Evaluable Analysis Set (EAS) will include all subjects who entered the study with Baseline measure and at least 1 post-baseline measures available. The data set will be used for PRO measures.
- The Re-Treatment Analysis Set (RAS) will include all subjects who received at least 1 dose of pexidartinib in the **Treatment-Free/Re-Treatment Cohort** after stopping pexidartinib. The data will be used for both efficacy and safety analyses for re-treated subjects in the **Treatment-Free/Re-Treatment Cohort**.

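### The Treatment-Free PRO endpoint also covers Re-Treatment quarters, and no described change analysis isolates the Screening-to-restart change

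*Combined protocol and SAP*

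**What the plan says.** **Endpoint definition.** In Table 3.1 (Section 3) and the synopsis (Section 1.1), the PRO row of the Treatment-Free period gives the mean change in PROMIS PF and EQ-5D-5L "quarterly for the treatment-free and Re-Treatment periods", with Screening values as Baseline. A separate Re-Treatment row in both places covers the Re-Treatment quarters again, with Baseline reset at entry to re-treatment.

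**Neighbouring safety row.** The Treatment-Free AE measure in the same table does stop at restart. It counts subjects with "any AE collected between Screening and start of re-treatment or final database lock (whichever occurs first").

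**Analysis.** Section 9.5.1.2 states: "The mean change from Baseline for these measures will also be reported over time along with its 95% CI by each cohort". The analysis set is the Evaluable Analysis Set (EAS), defined in Section 9.4 as "all subjects who entered the study with Baseline measure and at least 1 post-baseline measures available". For the Re-Treatment Analysis Set (RAS), "the Baseline measure of the retreated subjects is defined as the latest measure prior to or on the date of re-treatment of pexidartinib".

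**Deferral.** Section 9.5.1 says that Tables 3.1 and 3.2 "list the primary and secondary endpoints and their corresponding definitions of all endpoints". It leaves detailed censoring rules for the primary and applicable secondary endpoints to the SAP, which per Section 9.5 "will be developed and finalized before database lock". The text available for this review contains no SAP rule that settles the point.

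**The concern.** PRO change while off drug is a named secondary objective of a study about stopping and restarting pexidartinib. A reader will take the Treatment-Free row as the answer to how patients function after stopping. If that row includes quarters after restart, it answers a different question: how patients fare under stopping with the option to restart. That is a valid summary, but not the one the row is filed under.

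The distinction matters because restart is discretionary and may follow a worse PRO score. The synopsis says: "Tumor assessment, subjective and/or functional measures, and safety will be considered in the decision-making process". Section 4.2 assumes that re-treatment will stabilise the disease and may shrink it. If some subjects decline, restart and then improve, their on-drug scores would pull the later cohort means back towards Screening. The RAS change analysis would not show the earlier loss, because it starts from the value already reached at restart.

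**Working it through.** The plan gives no PRO figure, restart rate or sample-size basis, so there is no stated number to reproduce. The check has two parts.

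**1. Text side by side**

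- *Which quarters?* The Treatment-Free PRO row names both periods. The Treatment-Free AE measure beside it ends at restart. The Re-Treatment PRO row covers the later quarters a second time.
- *Which baseline?* The Re-Treatment quarters therefore have two: Screening in one row, BL-2 in the other.
- *Which visits enter the cohort mean?* The EAS definition selects subjects, not visits. Section 9.5.2 assigns each AE to the period in which it started. Section 9.5.1.2 has no equivalent rule for PROs in the EAS analysis.
- *Which time axis?* Table 1.3 numbers Re-Treatment visits from BL-2. The protocol does not say how these map to months since Screening.
- *What shows Screening-to-restart change?* The EAS analysis does not single out restarters, and the RAS change begins at the last value before or on restart. Raw BL-2 scores may appear in the RAS summaries, but a raw score is not a within-subject change.

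**2. Illustration at a single late visit**

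All inputs are assumptions. Every restarter is taken to have restarted before this visit.

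- r = share of the cohort that has restarted
- d = points lost by restarters from Screening to BL-2
- ρ = share of d recovered on drug
- m = mean change in subjects still off drug

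Formulas:

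- Each restarter's BL-2 value kept: (1 − r)m − r·d
- All-visits cohort mean: (1 − r)m − r·d·(1 − ρ)
- Difference between the two: r·d·ρ, which does not depend on m
- Mean of subjects still off drug at the visit: m

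With r = 0.4 and m = −1, the first term is 0.6 × (−1) = −0.6. For d = 6, the BL-2-kept mean is −0.6 − 0.4 × 6 = −3.0. The all-visits mean at ρ = 0.5 is −0.6 − 0.4 × 6 × 0.5 = −1.8.

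| d | BL-2 kept | All visits, ρ = 0 | ρ = 0.5 | ρ = 1 | Still off drug only |
|---|---|---|---|---|---|
| 0 | −0.6 | −0.6 | −0.6 | −0.6 | −1.0 |
| 3 | −1.8 | −1.8 | −1.2 | −0.6 | −1.0 |
| 6 | −3.0 | −3.0 | −1.8 | −0.6 | −1.0 |

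Over r = 0.3 to 0.5 and d = 0 to 8, the difference r·d·ρ is 0 with no recovery, 0 to 2.0 points at half recovery (maximum 0.5 × 8 × 0.5) and 0 to 4.0 points at full recovery (maximum 0.5 × 8 × 1).

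Two things follow. There is no masking if d = 0 or ρ = 0. And cutting the series at restart is not enough by itself: at d = 6 the mean of those still off drug is −1.0 against −3.0, because the subjects who left the off-drug group were the ones who had declined.

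The BL-2-kept mean is a reference point, not a true value. Restarters picked at a low score may partly regress towards their usual level without any drug effect.

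**The case against.** A reader might infer that the plan will average off-drug and on-drug scores and so conceal the decline after stopping. The documents do not support that, for four reasons.

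- **The wording has another reading.** Naming both periods could mean that each is reported separately. The tables are organised by period, the two periods have separate visit schedules, and the RAS analysis already takes its own baseline. Without a mapping to months since Screening, a pooled by-visit mean is not fully specified either. This stands: pooling is the literal reading, not a declared intention.
- **The SAP may settle it.** Censoring rules for applicable secondary endpoints are deferred to the SAP, and a cut at restart could be one of them. This stands in part. Section 9.5.1 still takes the endpoint definition from Table 3.1, so a SAP that split the periods would depart from that row, and one that followed it would not.
- **The analysis is over time.** PROs are collected at Month 1 and then quarterly while off drug, so a restarter's decline enters the cohort mean at the visits where it occurred. This stands. Masking is partial and concerns later time points; the formulas above describe one such visit, not the whole series.
- **The size is assumed.** No restart rate, decline or recovery is given, and Section 4.2 speaks of disease stabilisation and possible shrinkage, not of PRO recovery. This stands in full.

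It would also go too far to say that the last-off-drug change must be the main summary. It mixes follow-up times and is open to regression to the mean. Choosing it as the principal estimand is a preference that the documents do not dictate.

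What remains is a row definition that conflicts with its own period label and with the AE measure beside it, and a missing Screening-to-restart change.

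**Conclusion.** The point holds in a limited form. The Treatment-Free PRO endpoint is defined over Re-Treatment quarters that another row takes from a different baseline, Section 9.5.1.2 does not separate the periods, and no described change analysis isolates what restarters lost between Screening and restart. Those are facts of the text.

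Understatement of off-drug worsening is a possibility, not a finding. It requires that restarters declined on the PRO and then recover on drug, and it affects only later time points. The range of 0 to 4.0 points rests wholly on assumed inputs, and its upper end needs every input at its extreme.

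The study is descriptive, with no hypothesis or p-values, so no error rate or sample size is touched. This is a modest but worthwhile improvement to the interpretation of a secondary endpoint.

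**What to change.** 1. In Table 3.1 and the synopsis, limit the Treatment-Free PRO endpoint to assessments up to and including the last one on or before re-treatment (BL-2). Report the Re-Treatment quarters in the RAS, indexed from BL-2.
2. In Section 9.5.1.2, report the Treatment-Free period separately, with the number of subjects still off drug at each visit. Alongside that by-visit summary, add the Screening-to-last-off-drug change for all EAS subjects in the cohort and the Screening-to-BL-2 change for restarters. Note that the former mixes follow-up times and that restarters chosen at a low score may partly regress. Neither addition need be made the main estimand.
3. If the all-visits cohort mean is kept, label it as the summary of stopping with the option to restart.

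The cost is wording in two tables and one section, mirrored in the SAP, plus a few descriptive tables. Table 1.3 already schedules both PRO instruments at BL-2, so no new data are needed.
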